5.7.2 Clinical Laboratory Evaluations

Blood will be collected within 6 months prior to the patient receiving the first dose of Replagal and at the biannual/annual safety visits for the following assessments: creatinine, glucose, blood urea nitrogen (BUN), potassium, sodium, chloride, bicarbonate, and fasting lipids profile (total cholesterol, HDL cholesterol, LDL cholesterol, and triglycerides).

The observed values and change from baseline will be summarized by biannual visit for laboratory data using descriptive statistics. Shift tables will also be presented comparing the baseline values to those at each biannual visit. Shifts over time will be presented by low, normal, and high. The numbers (and percentages) of patients within each category will be tabulated. Lab assessments will be summarized by cohort, previous ERT status and overall based on the safety population.

Any patient, who had a clinically significant abnormal value, as determined by the investigator, will be listed.

All laboratory data from both scheduled and unscheduled (i.e., unexpected) visits will be presented in the data listings for the safety population. However, for the summary tables only laboratory data associated with scheduled visits will be summarized.

If there are repeated or retest laboratory measurements associated with a given study visit then, in general, the second set of measurements with respect to date/time order, will be used for the statistical analysis unless the values are invalid or missing. In this instance a value from the first set of measurements will be used provided it is valid and non-missing.

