7.5 Adverse Events and Other Safety Assessments

Adverse event tabular summaries will be based on all treatment-emergent AEs recorded; AEs will be coded using the Medical Dictionary for Regulatory Activities coding dictionary.

Adverse events will be summarized by system organ class (SOC) and preferred term (PT). The total number of AEs by SOC and PT, as well as the number and proportion of patients experiencing an AE, will be tabulated by cohort; a patient will be counted only once within each SOC and PT. Adverse events by SOC and PT will be tabulated by cohort and severity. In the case of multiple occurrences of the same AEs (at the preferred term level) in an individual patient, the AE that is classified as the most severe (ie, maximum severity) will be identified for the analysis by severity. In addition, AEs by SOC and PT will be tabulated by cohort and relationship to study drug by reporting the episode with the closest relationship to study drug.

The number and percentage of patients reporting SAEs will be presented by cohort, SOC, and PT; in addition, an SAE listing will be presented.

The number and percentage of patients reporting an infusion-related reaction will be presented by cohort, SOC, and PT. An infusion-related reaction is defined as an AE that: (1) begins either during or within 12 hours after the start of the infusion and (2) is judged by the investigator to be possibly or probably related to study drug.

The number and proportion of patients experiencing an AE(s) that led to permanent discontinuation will be summarized by cohort, SOC, and PT. Furthermore, a listing of all patients who permanently discontinued due to an AE(s) will be provided.

Furthermore, safety will be evaluated by assessing vital signs and blood tests. Data for vital signs and blood tests will be listed for each patient and abnormal values will be flagged. Shift tables from baseline to last visit may be presented for vital signs, and a summary table may be presented for blood tests.

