3 STUDY DESIGN

3.1 General Description

This is an open-label, single-arm, multicenter, Phase III/IV safety study and is designed to evaluate the safety of Replagal in Canadian patients with Fabry disease. All patients may continue to receive Replagal in this treatment plan until Replagal AF is commercially available for the patient, the patient's participation or the study is discontinued, whichever comes first. Safety data will be collected throughout the treatment protocol.

A minimum of 60 patients with Fabry disease and up to 200 patients are expected to participate in this protocol. Two cohorts are included in the protocol; Cohort 1 is for patients from the Canadian Fabry Disease Initiative (CFDI) and provides Replagal treatment on an every other week (EOW) regimen and cohort 2 is only for patients who participated in REP001a and provides Replagal treatment on a weekly regimen. Patients may begin to enroll in the treatment protocol as soon as the eligibility criteria are fulfilled and informed consent is obtained.

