3.6 Determination of Sample Size

Health Canada requested that a minimum number of patients be specified in order to obtain meaningful safety data from this safety clinical trial. With a minimum of 60 subjects, there will be at least a 95% chance of observing at least one adverse event (AE) of a given type, if the event has a frequency of 5%.

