5 STATISTICAL ANALYSIS

5.1 General Methodology

All analysis will be performed by the Biometrics Department, Shire HGT using SAS[®] Software version 9.3 or higher (SAS institute, Cary, NC, USA). All study data will be presented in by-patient data listings.

No formal statistical tests will be conducted. Tabular summaries of patient baseline demographic and clinical characteristics, patient disposition, medical history, vital signs, AEs, anti-agalsidase alfa antibody, and infusion information will be produced for the safety population. The safety population includes all patients who receive at least one full or partial infusion of Replagal. Continuous data collected prior to receiving study drug and at subsequent visits will be summarized using descriptive statistics (n, mean, median, minimum, maximum, and standard deviation). Categorical data will be summarized as frequencies and percentages. All data summaries will be presented for each cohort and overall, as appropriate, unless otherwise indicated

Cohort:

Cohort is defined as:

- Cohort 1: Patients from CFDI and receiving Replagal on EOW regimen
- Cohort 2: Patients who participated in REP001a and receiving Replagal on weekly regimen

Data Derivations:

The following key derived and computed variables have been initially identified. It is expected that additional variables may be required. The SAP will not be amended for additional variables. All derived and computed variables, including additional variables later identified, will be documented in the “Define Document,” and also in the SAS analysis dataset creation programs. The following are anticipated data derivations:

- *Screening period:* Within 6 months prior to first dose
- *Pre-treatment period:* Prior to first study drug infusion
- *Day 1:* Day of first study drug infusion
- *Date of Enrollment (entry):* Date informed consent is signed
- *Baseline:* Last valid non-missing assessment made prior to the first study drug infusion.
- *Change from Baseline:* Post-baseline value – Baseline Value

- *% Change from Baseline:* $\{(Change\ from\ Baseline / Baseline) * 100\}$
- *Change from Pre-infusion:* Value immediately after infusion – value immediately before infusion.
- *% Change from Pre-infusion:* $\{(Change\ from\ pre-infusion / pre-infusion) * 100\}$
- *Age:* integer of $\{(date\ of\ informed\ consent - date\ of\ birth) / 365.25\}$
- *Duration of study drug exposure:* (Date of last infusion – date of first infusion)+1

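### Laboratory tables are by visit only, so no planned table counts the patients who ever developed an out-of-range value on treatment, beyond those reported as adverse events

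*SAP*

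**What the plan says.** SAP 5.7.2 plans two kinds of laboratory table.

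- **Descriptive statistics** of the observed value and the change from baseline, by biannual visit. Under SAP 5.1 these include the minimum and maximum.
- **Shift tables**: "Shift tables will also be presented comparing the baseline values to those at each biannual visit". The categories are three: "Shifts over time will be presented by low, normal, and high".

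Both are split by cohort, previous ERT status and overall. The same section says that "for the summary tables only laboratory data associated with scheduled visits will be summarized"; unscheduled results go to listings. Where a test is repeated at a visit, the second set of results is generally analysed, and the first is used only if the second is invalid or missing.

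Patient-level laboratory output consists of listings: all laboratory data, and patients with a value the investigator judged clinically significant. Protocol 7.5 has the same character: "Data for vital signs and blood tests will be listed for each patient and abnormal values will be flagged". It makes a blood-test summary table optional and does not state its content.

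Other safety data do get a patient-level count over the whole study. SAP 5.7.1 counts each patient once per SOC and PT for TEAEs, at maximum severity in the severity table. SAP 5.7.5 tabulates antibody positivity at each visit and also overall.

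**The concern.** A by-visit shift table shows how many of the patients sampled at that visit are abnormal then. It does not show how many different patients became abnormal at some time. One patient with a persistent abnormality appears in every visit's table. Several patients with transient abnormalities at different visits can produce exactly the same tables.

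Safety is the study's only objective, and blood tests are a named safety assessment. A reader of the study report will want to know how many patients moved outside the reference range on treatment, in which direction, and from what baseline status. As planned, the tables leave that unanswered unless the investigator reported the change as an adverse event.

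The tables also lean towards normal results. Protocol 6.10.1.1 asks that an out-of-range test be repeated until the result normalises or has an explanation. If the repeat belongs to the same visit, SAP 5.7.2 generally tabulates the repeat. If the abnormal result came from an unscheduled draw, it is not tabulated.

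**Working it through.** **The plan's own figure.** SAP 3.6 gives at least a 95% chance of seeing one or more events of 5% frequency in 60 patients. This reproduces: 1 − 0.95^60 = 0.954. It is a statement about patients with at least one event. It concerns adverse events, and the point here does not depend on it.

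**Inputs.**
- Number of patients N: 60 and 200, from SAP 3.1 ("A minimum of 60 patients with Fabry disease and up to 200 patients are expected to participate in this protocol").
- Share q abnormal at each visit: 5% and 10%. These are assumptions; the documents give no laboratory abnormality rates.
- Number of visits k: 2, 4 and 8. These are assumptions; treatment is open-ended and visits are biannual or annual. Four biannual visits span 2 years and eight span 4 years; eight annual visits span 8 years. For scale, the original protocol is dated September 2010 and Amendment 5 March 2015, about four and a half years apart.
- Simplification: every patient is normal at baseline and sampled at every visit.

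**Formulas.** Let m = N × q be the number abnormal at each visit.
- Fewest patients ever abnormal (the same patients each time): m.
- Most patients ever abnormal (different patients each time): min(N, k × m).
- Expected number if visits were independent: N × (1 − (1 − q)^k).

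| N | q | k | Seen at each visit | Fewest ever | Most ever | Independent |
|---|---|---|---|---|---|---|
| 60 | 5% | 2 | 3 | 3 | 6 | 5.9 |
| 60 | 5% | 4 | 3 | 3 | 12 | 11.1 |
| 60 | 5% | 8 | 3 | 3 | 24 | 20.2 |
| 200 | 5% | 4 | 10 | 10 | 40 | 37.1 |
| 60 | 10% | 4 | 6 | 6 | 24 | 20.6 |

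As shares, 5% at each of 8 visits gives a range from 5% to 8 × 5% = 40%; independence gives 1 − 0.95^8 = 33.7%. Within each row, the fewest, independent and most cases share the same number abnormal at every visit, so the visit tables cannot tell them apart.

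**What the bounds leave out.** They cover only the values that reach the tables. Abnormal results from unscheduled draws, and first results replaced by a retest, could take the true count above the upper bound. Patients seen yearly would also be missing from some half-yearly tables, so denominators would change between visits.

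**The case against.** The strongest case against is that this is a matter of layout in a descriptive, single-arm study: "No formal statistical tests will be conducted". Nothing in the documents commits the sponsor to a worst-value shift. Much of that case stands, and it rules out several stronger readings that a reader might infer.

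- *That the shift table is the only quantitative laboratory display.* It is not. The descriptive statistics print the extreme scheduled value and extreme change at each visit, so how large the changes were is partly answered. How many patients were affected is not.
- *That abnormal laboratory values are counted nowhere by patient, or that a peak between visits reaches no table.* Protocol 6.10.1.1 includes abnormal laboratory values among adverse events, and the TEAE tables count each patient once per preferred term over the treatment period. A peak reported as an adverse event is therefore counted. But that route depends on investigator judgement and covers less than all out-of-range values.
- *That information is lost.* All laboratory data are listed. With 60 to 200 patients the count could be made by hand. A listing is still not a summary, and a count made after the event would follow no stated rule for retests or unscheduled draws.

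Two further cautions stand. Ever-abnormal counts rise with the number of samples and the length of follow-up, both of which will differ between patients. Cohort 1 patients may also qualify through reduced or falling GFR, so a high creatinine or urea may reflect Fabry disease. Both limit how the count is interpreted; neither is a reason to leave it out.

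**Conclusion.** The point holds as a reporting gap. No table in SAP 5.7.2 gives a once-per-patient count of new reference-range abnormalities on treatment, and the by-visit tables cannot be combined to give one. The optional blood-test table in Protocol 7.5 does not close the gap, because it is neither committed nor specified.

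The size of the gap depends on how persistent abnormalities are, which the documents do not say. Under the assumed figures the visit tables leave a fourfold range over 4 visits (3 to 12 of 60) and an eightfold range over 8 visits (5% to 40%). These ranges show what the tables cannot resolve. They do not predict this study's abnormality rates.

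The sample-size statement, the adverse event tables and the data collected are unaffected. The documents do not support a claim that laboratory safety goes unreported. The change is worth making before database lock because it determines whether a safety-only study can report this count from a planned table.

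**What to change.** Keep the by-visit tables. Add to SAP 5.7.2, for each of the 11 analytes (creatinine, glucose, urea nitrogen, potassium, sodium, chloride, bicarbonate, total, HDL and LDL cholesterol, triglycerides), two low/normal/high shift panels: baseline to the highest, and baseline to the lowest, valid value per patient.

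- **Window:** first study infusion to 30 days after the last dose, matching the TEAE period in SAP 5.7.1.
- **Values:** scheduled, unscheduled and first-test results. A first result superseded by a retest still counts unless it is documented as invalid.
- **Lipids:** fasting samples only.
- **Denominator:** patients with a baseline and at least one post-baseline value.
- **Presentation:** by cohort and overall, with median samples and median follow-up per patient beside the counts.

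The cost is two panels per analyte, 11 × 2 = 22 in all, from data already collected and listed. No new procedure is needed. The SAP should say that the counts are descriptive, rise with the number of samples and partly reflect the underlying disease.

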1 INTRODUCTION

1.1 Overview of Fabry Disease

Fabry disease is a rare, progressive, debilitating, glycosphingolipid storage disorder. It is caused by deficient activity of the lysosomal enzyme α -galactosidase A, which results from a mutation in the α -galactosidase A (GLA) gene, located on chromosome Xq22.1. α -galactosidase A cleaves galactose in the alfa-anomeric configuration from glycosphingolipids, in particular globotriaosylceramide (Gb₃).¹ Mutations in the GLA gene lead to decreased or complete absence of enzyme activity that, in turn, result in accumulation of varying amounts of Gb₃ in cells in vascular beds, cardiomyocytes, and various other cells, tissues, and organs throughout the body. The clinical manifestations of Fabry disease typically include angiokeratomas, acroparesthesias, anhydrosis, anhedonia, chronic renal insufficiency leading to renal failure, hypertrophic cardiomyopathy with arrhythmias and infarction, and microvascular cerebral events including transient ischemic attacks (TIAs), stroke, and dolichoectasia.² In general, patients with complete absence of GLA have a classic phenotype with rapidly progressing renal, cardiac, and cerebrovascular events whereas patients with reduced GLA have an attenuated clinical phenotype.³

Clinical onset of Fabry disease typically occurs during childhood or adolescence with recurrent episodes of severe neuropathic pain in the extremities, characteristic cutaneous lesions known as angiokeratomas, and a distinctive but asymptomatic corneal dystrophy termed cornea verticillata. Vital organs, especially the heart, kidneys, and brain, are progressively affected with increasing age.⁴

In contrast to classical X-linked disorders, females may also be affected, presumably from biased X-linked inactivation and lack of cross-cellular correction of lyonized cells by normal cells. Females may inherit an X-linked Fabry mutation from either parent and are not asymptomatic carriers. Females account for twice the number of male patients. Clinically, manifestations in females range from mild to severe phenotypes.^{5,6} The onset of symptoms and age of diagnosis in females occur approximately 10 years later than in males.⁷

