4 POPULATION SELECTION

The population consists of Canadian patients with Fabry disease.

Each patient in Cohort 1 must meet the following criteria to receive treatment (inclusion criteria for Cohort 1 are consistent with the CFDI):

1. The patient has a documented diagnosis of Fabry disease.
2. The patient is sufficiently compliant with study activities to participate in this treatment plan, as judged by the investigator.
3. The patient must meet current Canadian guidelines for ERT for Fabry disease ¹⁵ by meeting any of the following criteria:
 - a. Age-adjusted glomerular filtration rate (GFR) <80 mL/min or a decline in GFR of >10% that is sustained for 3 months and for which other causes of declining renal function have been excluded by a nephrologist or any 2 of the following:
 - Isolated proteinuria ≥ 500 mg/day/1.73 m² without other cause
 - Nephrogenic diabetes insipidus
 - Fanconi syndrome
 - Hypertension
 - b. Evidence of cardiac involvement related to Fabry disease including any 2 of the following:
 - Left ventricular (LV) wall thickness >12 mm
 - Left ventricular hypertrophy by electrocardiogram (ECG); Estes ECG score must be >5
 - Left ventricular mass index by 2-dimensional (2D) echocardiogram 20% above normal for age
 - Diastolic filling abnormalities by 2D echocardiogram or other accepted measures of diastolic filling. E/A ratio >2.0 and deceleration time <140 msec
 - Increase of LV mass of at least 5 g/m²/year, with 3 measurements over a minimum of 12 months
 - Increase of left atrium (LA) size on 2D echo at least 10% above normal for age. In parasternal long axis view >33 mm; in 4-chamber view >42 mm
 - Cardiac conduction and rhythm abnormalities: AV block, short PR interval, left branch bundle block (LBBB), ventricular or atrial tachyarrhythmias, sinus bradycardia (in the absence of drugs with negative chronotropic activity)
 - Delayed posterolateral LV wall late enhancement on magnetic resonance imaging as evidence of advanced cardiac disease with fibrosis.
 - c. Evidence of neurological involvement related to Fabry disease, including 1 of the following:
 - Stroke or TIA prior to the age of 55 documented by a neurologist
 - Acute onset unilateral hearing loss

- Acute monocular visual loss without other cause
- d. Chronic, intractable diarrhea and/or abdominal pain/cramps, refractory to standard management for at least 6 months

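### The creatinine low/normal/high shift table cannot show worsening within High, and with no eGFR or fold-change summary and no dialysis/transplant rule, on-study renal failure can be counted as improvement.

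*SAP*

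**What the plan says.** SAP 5.7.2 lists the analytes as "creatinine, glucose, blood urea nitrogen (BUN), potassium, sodium, chloride, bicarbonate, and fasting lipids profile". Creatinine and BUN are the only ones that measure renal function directly.

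The section plans four displays:
- Continuous summaries: "The observed values and change from baseline will be summarized by biannual visit for laboratory data using descriptive statistics". SAP 5.1 defines descriptive statistics to include median, minimum and maximum.
- Shift tables from baseline to each visit: "Shifts over time will be presented by low, normal, and high".
- A listing of patients with an abnormal value that the investigator judges clinically significant.
- Listings of all laboratory data. Unscheduled values appear here but are kept out of the summary tables.

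SAP 5.1 also defines percent change from baseline as a derived variable, but 5.7.2 does not apply it to laboratory data.

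On the population, one route into Cohort 1 (Protocol 4) is "Age-adjusted glomerular filtration rate (GFR) <80 mL/min or a decline in GFR of >10% that is sustained for 3 months". Protocol 1.1 names "chronic renal insufficiency leading to renal failure" among the typical manifestations of the disease. The exclusion criteria in Protocol 4 do not mention dialysis or transplantation.

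**The concern.** Safety is the study's only objective, and the disease damages the kidney. Patients may enter with reduced renal function, and dosing is open-ended, so renal events have time to accrue. Three features of the laboratory plan matter here.

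- A three-level shift has no cell for further deterioration once a patient is High.
- Absolute change in creatinine is hard to read across patients. A rise of 50 micromol/L is a ratio of 110/60 = 1.83 from a baseline of 60, but 350/300 = 1.17 from a baseline of 300. No eGFR or ratio summary corrects for this.
- Creatinine falls after renal replacement because the kidney's work has been taken over, not because the patient's own kidneys have recovered. With no rule for such values, a patient who reached renal failure on study can add a High-to-Normal shift and a large negative change.

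At stake is whether two of the planned laboratory tables could read as reassuring when the renal course was poor. SAP 1.2 says these analyses go into regulatory submissions.

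**Working it through.** **The plan's own figure.** The only numerical design statement (SAP 3.6) is a chance of at least 95% of seeing one or more AEs of a type with 5% frequency among 60 patients. It reproduces: 1 - 0.95^60 = 0.9539. It says nothing about creatinine, and nothing below affects it.

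**Does any rule govern values after renal replacement?**
- SAP 5.7.2: the retest rule only chooses between repeat measurements at one visit. Scheduled values go into the summaries.
- SAP 7.2: covers missing values, partial dates and early-termination data.
- SAP 5.1 and 7.7: an outlier is an obvious error or a medically implausible value. A post-transplant creatinine is neither, and outliers stay in the main analysis anyway.
- Protocol 6.13: the comorbidity ground for withdrawal is limited to conditions unrelated to the disease under study, so Fabry renal failure does not fall under it. Withdrawal for an AE is a matter of judgement.

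Nothing excludes these values, so they enter by default. This is inferred from silence; the SAP does not state it as a rule.

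**Illustration.** Every creatinine value and count here is assumed; only N = 60 comes from the documents. Units are micromol/L and the upper limit of normal is taken as 110. At baseline 40 patients are at 80, 17 at 160 and 3 at 600. A doubling is 160 to 320; an on-study transplant is 600 to 105; everyone else is unchanged. Mean change = (160 x doublings - 495 x transplants) / 60.

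| Doublings | Transplants | Normal to Normal | High to High | High to Normal | Mean change | Median | Min | Max |
|---|---|---|---|---|---|---|---|---|
| 0 | 0 | 40 | 20 | 0 | 0 | 0 | 0 | 0 |
| 3 | 0 | 40 | 20 | 0 | +8.0 | 0 | 0 | +160 |
| 6 | 0 | 40 | 20 | 0 | +16.0 | 0 | 0 | +160 |
| 6 | 1 | 40 | 19 | 1 | +7.8 | 0 | -495 | +160 |
| 6 | 2 | 40 | 18 | 2 | -0.5 | 0 | -495 | +160 |
| 6 | 3 | 40 | 17 | 3 | -8.8 | 0 | -495 | +160 |

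- Rows 1 to 3: the shift table is identical with 0, 3 or 6 doublings. The mean registers them. The maximum shows that someone doubled, but not how many.
- Rows 4 to 6: each transplant adds an apparent improvement to the shift table and pulls the mean down until it changes sign. The minimum of -495 and the maximum of +160 still show that something happened in both directions.

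**A milder assumed case.** Transplanted patients go from 300 to 110 and all others are unchanged. The mean change is 1 x (-190)/60 = -3.2, 2 x (-190)/60 = -6.3 or 3 x (-190)/60 = -9.5. At the upper enrolment of 200, three such patients give 3 x (-190)/200 = -2.9.

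**What a ratio table would add.** Each doubling has ratio 320/160 = 2.0, so rows 2 and 3 would show 3 and 6 patients in the top category (2 or more). A patient going from 180 to 400 has no shift but a ratio of 400/180 = 2.2.

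**The case against.** A reader might infer that renal safety rests on the shift table and that worsening in already-High patients cannot be seen at all. The documents do not support that. SAP 5.7.2 offers the shifts in addition to observed values and change from baseline, and the 180-to-400 patient would show as +220 there and appear in the listings. Protocol 6.10.1.1 makes worsening of an existing condition an AE. Events requiring hospitalization are SAEs, and both are tabulated by SOC and PT and by severity (SAP 5.7.1). New renal failure leading to transplant should therefore be reported. A rise at a scheduled visit before the transplant would also appear in the by-visit table.

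Other fair points: the illustration is invented; the study is descriptive ("No formal statistical tests will be conducted"); and Protocol 7.5 only says that a blood-test summary may be presented, so the SAP already goes further than the protocol.

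Most of this stands, and it limits the point to the laboratory tables. It does not remove it. The maximum does not count patients, and the median stays at 0 in every row above. The clinically significant listing depends on investigator judgement, and listings are not summaries. No planned table brings together patients who reached renal failure, dialysis or transplant. Laboratory summaries are by cohort, previous ERT and overall, so adults and children are pooled on raw creatinine.

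**Conclusion.** The point holds for the creatinine tables. That the shift table cannot show worsening within High follows from its three categories and needs no assumption. That values after on-study dialysis or transplant can count as improvement rests on the SAP's silence and on such patients remaining on study with scheduled samples, which neither document prevents.

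The size is unknown. The documents give no baseline creatinine distribution, no reference limit and no number starting renal replacement. Even the share starting High is uncertain: reduced GFR is one of several entry routes, and a GFR slightly below 80 mL/min need not put creatinine above its range. The figures above show direction and mechanism only.

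It would go too far to conclude that the overall safety result is biased by a known amount, or that a poor renal course would go unreported. The AE/SAE tables and the listings are separate routes. This is a worthwhile improvement to the safety read-out, best made before database lock; it does not undermine the study.

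**What to change.** Amend SAP 5.7.2 as follows.

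1. **Renal replacement starting after baseline.** Flag the patient and count them in a separate row of the renal summary. Present their later creatinine and BUN apart from the main change and shift summaries: list them, and show the summaries with and without them. Keep patients transplanted before entry in the summaries as an identified group; dropping every post-transplant value would remove them entirely and hide any graft decline. Simply deleting on-study cases would also leave later visits to patients with better kidneys, which is why both versions are needed.
2. **eGFR change from baseline in adults.** Derive it from creatinine, age and sex, all already collected, and name the equation. Extend it to patients under 18 only if follow-up height is confirmed to be in the CRF. Protocol 6.5 schedules height within the physical examination, but SAP 5.7.4 says physical examination data are not in the CRF, and SAP 5.7.3 summarizes height at baseline only. If it is extended, state the rule for patients who turn 18 on study.
3. **Creatinine ratio to baseline in adults.** Use categories <1.5, 1.5 to <2 and >=2, by visit and as the highest on-treatment value. Add this to the shift table; replacing that table would lose the Normal-to-High shifts. Restricting it to adults avoids flagging normal growth in children.

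**Cost.** SAP wording, two derived variables and one or two more tables, with no new samples and no change to the sample size. Dates of dialysis or transplant should be obtainable from AE/SAE and medical history records, which should be confirmed against the CRF. One limitation remains: the highest on-treatment ratio depends on the number of measurements, and visits may be biannual or annual, so it should be read next to the by-visit table.
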